1 PROTOCOL SYNOPSIS

Trial Sponsor	Alcon Research, Ltd. [name]
Name of Test Product	DD T2
Name of Control Product	CooperVision® clariti® 1 day (Clariti 1 Day)
Title of Trial	Clinical Comparison of Two Daily Disposable Soft Contact Lenses
Protocol Number	CLE383-C006
Number of Sites	~1
Country	US
Planned Duration of Exposure	~20 days total duration 
 • Test Product: 8 days (-1/+2 days) • Control Products: 8 days (-1/+2 days)
Number of Subjects	Target to complete: 20
	Planned to enroll: ~22
Study Population	Volunteer subjects aged 18 or over who are soft daily disposable contact lens wearers (excluding current Clariti 1 Day wearers), have at least 3 months of contact lens wearing experience, and who wear their habitual lenses at least 5 days per week and at least 8 hours per day.
Objectives	The primary objective of this study is to evaluate the overall performance of DD T2 lenses when compared to Clariti 1 Day lenses.
Endpoints	Primary Effectiveness 
 • Overall quality of vision
	 
Safety
 
 • AEs • Biomicroscopy findings • Device deficiencies

Assessments
	
Effectiveness
 
 - VA (Snellen distance) 

 
 - Overall quality of vision 

 
Safety
 
 - AEs - Biomicroscopy - Device deficiencies 	

Study Design
	
 Prospective
 
 Single group
 
 Parallel group
 
 Crossover
 
 Other
 
 Contralateral
 
 Bilateral
 
 Monocular lens wear
	
 Single-masked (trial subject)
 
 Single-masked (Investigator)
 
 Double-masked
 
 Open-label
 
 Other
 
 Randomized


This is a randomized, prospective crossover study design. Approximately 22 subjects will be randomized to 1 of the 2 lens sequences consisting of 2 crossover sequences of test vs. control. Subjects will wear the assigned study Lens 1 bilaterally for approximately 1 week before crossing over into the assigned study Lens 2 bilaterally for approximately 1 week.
 
Study Visits:
 
 1. Baseline/Dispense Lens 1 2. Day 8 (-1/+2 days) follow-up Lens 1/Dispense Lens 2 3. Day 8 (-1/+2 days) follow-up Lens 2/Exit 		

Test Product Details
	
Primary component/material
	

Product Name
		
DD T2

	LID Number	LID006841
	Manufacturer	Alcon
	Other	The lenses will be available in -1.75 D to -4.50 D (0.25 D steps)
Control Product Details	Primary component/material	somofilcon A
	Product Name	Clariti 1 Day
	LID Number	LID014044
	Manufacturer	CooperVision
	Other	The lenses will be available in -1.75 D to -4.50 D (0.25 D steps)
Inclusion Criteria	
 1. Subject must be at least 18 years of age. 2. Subject must be able to understand and must sign an ICF that has been approved by an IRB. 3. Successful wear of daily disposable spherical soft contact lenses in both eyes for a minimum of 5 days per week and 8 hours per day during the past 3 months. 4. Manifest cylinder ≤ 0.75 D in each eye. 5. BCVA 20/25 or better in each eye. 6. Subject must be willing to stop wearing their habitual contact lenses for the duration of study participation. 	
Exclusion Criteria	
 1. Any anterior segment infection, inflammation, or abnormality or disease (including systemic) that contraindicates contact lens wear, as determined by the Investigator. 2. Any use of systemic or ocular medications for which contact lens wear could be contraindicated, as determined by the Investigator. 3. History of refractive surgery or plan to have refractive surgery during the study or irregular cornea in either eye. 4. Ocular or intraocular surgery (excluding placement of punctal plugs) within the previous 12 months or planned during the study. 5. Biomicroscopy findings at screening that are moderate (Grade 3) or higher and/or corneal vascularization that is mild (Grade 2) or higher. 6. Current or history of pathologically dry eye in either eye that, in the opinion of the Investigator, would preclude contact lens wear. 7. Current or history of herpetic keratitis in either eye. 8. Eye injury in either eye within 12 weeks immediately prior to enrollment for this trial. 9. Current or history of intolerance, hypersensitivity, or allergy to any component of the study products. 10. Wearing habitual contact lenses in an extended wear modality (routinely sleeping in lenses for at least 1 night per week) over the last 3 months prior to enrollment. 11. Any use of topical ocular medications and artificial tear or rewetting drops that would require instillation during contact lens wear. 12. The Investigator, his/her staff, family members of the Investigator, 	

	
family members of the Investigator's staff, or individuals living in the households of the aforementioned persons may not participate in the study.
 
13. Participation of the subject in a clinical trial within the previous 30 days or currently enrolled in any clinical trial.14. Currently wearing Clariti 1 Day contact lenses.15. Habitually wearing monovision or multifocal lenses during the last 3 months.
Associated Materials	Lubrication/re-wetting drops will not be permitted.

Table 1–1 Schedule of Study Procedures and Assessments

Procedure/ Assessment	Visit 1, Day 1	Visit 2, Week 1: Day 8 of lens wear (-1/+2 days)		Visit 3, Week 2: Day 8 of lens wear (-1/+2 days)	Unscheduled Visit	Early Exit
		Follow-up Lens 1	Dispense Lens 2			
	Baseline/ Dispense Lens 1	Follow-up Lens 1	Dispense Lens 2	Follow-up Lens 2/ Exit		
Informed Consent	✓	-	-	-	-	-
Demographics	✓	-	-	-	-	-
Medical History	✓	-	-	-	-	-
Concomitant Medications	✓	(✓)	-	(✓)	(✓)	(✓)
Inclusion/ Exclusion	✓	-	-	-	-	-
Habitual lens (brand, power)*	✓	-	-	-	-	-
VA w/ habitual correction (OD, OS, Snellen distance)*	✓	-	-	✓	(✓)	✓
Biomicroscopy	✓	✓	-	✓	✓	✓
Dispense study lenses	✓	-	✓	-	-	-
VA w/ study lenses (OD, OS, Snellen distance)	✓	✓	✓	✓	(✓)	(✓)

Procedure/ Assessment	Visit 1, Day 1	Visit 2, Week 1: Day 8 of lens wear (-1/+2 days)		Visit 3, Week 2: Day 8 of lens wear (-1/+2 days)	Unscheduled Visit	Early Exit
		Follow-up Lens 1	Dispense Lens 2			
Subjective rating with study lenses: 
 • [REDACTED] • [REDACTED] • [REDACTED] • [REDACTED] • overall quality of vision • [REDACTED] • [REDACTED] 	-	✓	-	✓	✓	✓
AEs	✓	✓	✓	✓	✓	✓
Device deficiencies	✓	✓	✓	✓	✓	✓
Exit Form	(✓)	(✓)	(✓)	(✓)	(✓)	(✓)

(✓) assessment performed as necessary, eg, decrease of VA by 2 lines or more with investigational product (IP)

* Source only

† Comments, optional

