3 INTRODUCTION

3.1 Study Rationale and Purpose

The purpose of this study is to obtain on-eye performance data to inform contact lens product development and to further evaluate product performance in the intended population. The primary endpoint was selected to fulfill the primary objective of the study. Procedures for measurement of these endpoints were selected based on common practice for these assessments. The design of this study is justified based upon preclinical and clinical testing, as described within the Investigator's Brochure. Clariti 1 Day contact lenses were chosen as the control product because these lenses have the same wear modality. The new contact lens in development is intended for the optical correction of refractive myopia in persons with non-diseased eyes.

There are no immediate plans to submit the results of this study for publication; however, the results may be offered for publication if they are of scientific interest, or if the results relate to a product that is subsequently approved or cleared for marketing.

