3.4 Subject Population

The study population includes approximately 22 volunteer subjects to be enrolled at approximately 1 site. The study population will consist of subjects with normal eyes (other than the need for optical correction for myopia), and who are adapted, existing wearers of daily disposable soft contact lenses in both eyes.

Subjects must be screened according to the full list of inclusion/exclusion criteria in Section 1 of this protocol. Rescreening of subjects is not allowed in this study.

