4.1 Identity of Study Treatments

Table 4-1 Description of Test and Control Products

	Test Lens	Control Lens
LID Number	LID006841	LID014044
Lens	DD T2	Clariti 1 Day
Material	██████	somofilcon A
Water Content	██████	56%
Base Curve (mm)	8.3	8.6
Diameter (mm)	14.2	14.1
Rx powers to be available in this study	-1.75 to -4.50 D (0.25 D steps)	-1.75 to -4.50 D (0.25 D steps)
Packaging, Labeling, and Supply	
 • Blister foil pack • Foil label includes at a minimum: 
 - material name and/or identifier - base curve - diameter - manufacturing protocol number - packing solution - power - lot number - expiration date - content statement - investigational device statement - Sponsor information - country of origin • Provided in boxes of 12 lenses per power per box, identified with the following at a minimum: 
 - a color coded label stating the protocol number - identifier - power - an investigational use only statement - tracking number • Lenses should be stored at room temperature. 	
 • Blister foil pack • Foil label includes at a minimum: 
 - material name and/or identifier - base curve - diameter - packing solution - power - lot number - expiration date - content statement - investigational device statement - Sponsor information - country of origin • Provided in boxes of 12 lenses per power per box, identified with the following at a minimum: 
 - a color coded label stating the protocol number - identifier - power - an investigational use only statement - tracking number • Lenses should be stored at room temperature.
Usage	
 • Wear: 
 ○ Daily wear ○ Bilateral, crossover group • Replacement period: Daily Disposable • Exposure: At least 8 hours per day, at least 5 days per week over the study treatment duration. • Lens Care: N/A 	

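### Does the eligibility list need a lens-power or myopia criterion because study lenses are supplied only from -1.75 to -4.50 D?

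*Protocol*

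**What the plan says.** The supply range appears in two places, both as product description. Under Test and Control Product Details in the synopsis, each lens carries the statement "The lenses will be available in -1.75 D to -4.50 D (0.25 D steps"), and Table 4-1 in Section 4.1 repeats the same range for both lenses.

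The target population is described in two further places. Section 3.1 says the test lens is "intended for the optical correction of refractive myopia in persons with non-diseased eyes". Section 3.4 says the study takes "subjects with normal eyes (other than the need for optical correction for myopia"), and adds: "Subjects must be screened according to the full list of inclusion/exclusion criteria in Section 1 of this protocol". It also says: "Rescreening of subjects is not allowed in this study".

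In the Section 1 list, the criteria closest to the point are:
- Inclusion 3: "Successful wear of daily disposable spherical soft contact lenses in both eyes", with minimum wearing time but no power.
- Inclusion 4: a limit on cylinder only.
- Inclusion 5: "BCVA 20/25 or better in each eye".
- Exclusion 15: rules out habitual monovision and multifocal wear.

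In Section 5.1.1, habitual lens power is recorded at step 4 and study lens power is determined at step 8. At step 9 the inclusion and exclusion criteria are reviewed, and the subject is either randomised or exited as a screen failure.

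**The concern.** Section 3.4 promises a myopic population and names the Section 1 list as the tool that delivers it, but the list contains no such condition. Step 9 ties both randomisation and screen failure to that list. Read literally, a hyperope, or a myope needing a power weaker than -1.75 D or stronger than -4.50 D, can meet every criterion and be randomised to lenses that do not exist in the required power. A site that sensibly declines has no numbered criterion to record.

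Three things could be at stake:
- a place in a small study, where about 22 are planned and 20 are to complete;
- precision, if completers fall below 20;
- the vision ratings themselves, if an ill-matched power were dispensed and the subject stayed in the analysis.

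**Working it through.** **1. Is the gap real?** Of the 6 + 15 = 21 criteria, none limits sphere, requires myopia or refers to the supplied range. Both lists are numbered without a break and show no redaction, so this is not lost text. The gap in wording is confirmed.

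**2. How narrow is the supply?** Number of powers = (4.50 - 1.75)/0.25 + 1 = 12 for each lens, all minus. Out-of-range candidates are therefore possible among spherical daily disposable wearers.

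**3. Would such a subject be randomised?** The Visit 1 order is: habitual power recorded (step 4), study lens power determined (step 8), eligibility reviewed and randomisation requested (step 9), lenses inserted (step 10). Step 8 cannot end in a study lens power that is not stocked. The investigator therefore knows before step 9 that the subject cannot be fitted, and has Sections 3.1 and 3.4 and Table 4-1 as written grounds for not proceeding. What is missing is only a numbered criterion under which to log the exit.

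**4. What if one slipped through unfitted?** The Safety Analysis Set, which is also the primary effectiveness set (Protocol Section 6.4), contains only exposed subjects. A subject never fitted is outside it. The cost is a place:
- allowance = 22 - 20 = 2, and 2/22 = 9.1%;
- one place = 1/22 = 4.5%.

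**5. What would a shortfall do to precision?** SAP Section 4.3.1 plans a two-sided 95% interval for the mean of each lens. Its half-width in SD units is t(0.975, n-1)/√n:
- n = 20: 2.093/4.472 = 0.468;
- n = 19: 2.101/4.359 = 0.482;
- ratio = 1.030, or 3.0% wider.

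Reaching 19 takes three losses from 22, and nothing in the documents attributes any of them to lens power.

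**6. What if an unsuitable power were dispensed?** No visible passage allows this. If it happened, both lenses share one range and each subject wears both, so the shortfall in correction would apply in both periods. Absolute ratings might fall, but no between-lens bias is shown.

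**7. Does any decision depend on it?** Protocol Section 6.4.1.1 formulates no hypotheses, and the SAP Executive Summary sets no success criteria.

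**The case for a change.** The strongest case for a change is that eligibility should not rest on staff departing from step 9 as written. Section 3.4 makes the Section 1 list complete, yet the list does not produce the population that Section 3.4 describes. One added sentence would restate a range already in the protocol and give these screen failures a recorded reason.

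The numbers can also be made to look worse. Suppose a share q of randomised subjects were out of range, every one of them were lost, and there were no other losses. The chance of 3 or more losses from 22 would then be 0.10 at q = 5%, 0.38 at 10%, 0.85 at 20% and 0.98 at 30%.

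The inconsistency in wording stands. The loss figures do not. Each q is an assumption with no support in the documents, and the calculation needs the site to randomise every subject it has just found it cannot fit. It is also tempting to set the 20/40 check at step 12 against the 20/25 entry criterion and call the first looser. They measure different things: binocular acuity in study lenses before leaving the office, and best corrected acuity in each eye at entry. The comparison says nothing about a missing power criterion.

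The added sentence would have little effect. The same subjects would leave at the same point in Visit 1 whether or not the reason carries a number. It would not cover power changes at the over-refraction in Visit 1 step 12 or Visit 2 step 10. Nor is it certain that no rule exists: Visit 1 steps 3, 5 and 6 are blacked out in the public copy, and the manual of procedures is not available.

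**Conclusion.** No change is called for. The eligibility list does omit the supplied power range and the myopic indication, and a sponsor who amends the protocol for another reason could tidy the wording. As it stands, this is missing detail that a site fills sensibly: power is fixed before randomisation, the range and the intended population are stated in the same protocol, and lenses outside the range cannot be handed out.

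The plausible cost is a screen failure without a numbered reason. The less plausible cost is one place of about 22 (4.5%), with no effect on who is analysed. No bias, loss of inference or change in conclusions is shown in a descriptive crossover with no success criterion.

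This rests on two assumptions: that the site, of which about one is planned, acts on what step 8 tells it, and that it does not dispense a power other than the one determined. Nothing in the visible text points the other way.

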1.1 Abbreviations

Table 1–2 Table of Abbreviations

Abbreviation	Definition
ADE	Adverse device effect
ASADE	Anticipated serious adverse device effect
AE	Adverse event
BCVA	Best corrected visual acuity
CFR	Code of Federal Regulations
D	Diopter
DD	Daily disposable
eCRF	Electronic case report form
EDC	Electronic data capture
FDA	US Food and Drug Administration
GCP	Good Clinical Practice
ICF	Informed consent form
IEC	International ethics committee
IP	Investigational product
IRB	Institutional review board
ISO	International Organization for Standardization
LID	Lens identification
mm	Millimeter
MOP	Manual of procedures
MR	Manifest refraction
N/A	Not applicable
OD	Right eye
OS	Left eye
OU	Both eyes
SAE	Serious adverse event
SADE	Serious adverse device effect
US	United States
USADE	Unanticipated serious adverse device effect
VA	Visual acuity

3 INTRODUCTION

3.1 Study Rationale and Purpose

The purpose of this study is to obtain on-eye performance data to inform contact lens product development and to further evaluate product performance in the intended population. The primary endpoint was selected to fulfill the primary objective of the study. Procedures for measurement of these endpoints were selected based on common practice for these assessments. The design of this study is justified based upon preclinical and clinical testing, as described within the Investigator's Brochure. Clariti 1 Day contact lenses were chosen as the control product because these lenses have the same wear modality. The new contact lens in development is intended for the optical correction of refractive myopia in persons with non-diseased eyes.

There are no immediate plans to submit the results of this study for publication; however, the results may be offered for publication if they are of scientific interest, or if the results relate to a product that is subsequently approved or cleared for marketing.

3.2 Trial Objective

The primary objective of this study is to evaluate the overall performance of DD T2 lenses when compared to Clariti 1 Day lenses.

3.3 Risks and Benefits

Contact lenses may offer improved peripheral vision and the convenience of not wearing spectacles. Material properties and design characteristics of the contact lens in development are features consistent with successful contact lens wear.

Based upon non-clinical testing and/or documented rationale for applicability of test results to the IP, the new contact lens in development is assessed to be non-toxic and biocompatible for on-eye use.

The new contact lens in development and the control contact lens are not intended for use with a cleaning/disinfecting solution, and the biocompatibility with lens care solutions and any associated clinical effects are unknown.

A summary of the known potential risks and benefits associated with the new contact lens in development can be found in the Investigator's Brochure. There may also be unknown risks with the use of the new contact lens. Risks are minimized by compliance with the eligibility criteria and study procedures, and through close supervision by a licensed clinician during

exposure to the study lenses. The potential harms associated with on-eye exposure to the new lens materials include toxicity response, blurred vision and ocular discomfort. In general, the risks with the new contact lens in development are anticipated to be similar to other marketed daily disposable soft contact lenses.

The site personnel will educate subjects on proper hygiene and lens handling, and compliance with the use of contact lenses according to the protocol. Subjects should be instructed not to wear contact lenses while sleeping or swimming. The site personnel will also advise the subjects to remove contact lenses and return for prompt follow-up of symptoms, such as ocular discomfort, foreign body sensation, excessive tearing, vision changes, or hyperemia.

3.4 Subject Population

The study population includes approximately 22 volunteer subjects to be enrolled at approximately 1 site. The study population will consist of subjects with normal eyes (other than the need for optical correction for myopia), and who are adapted, existing wearers of daily disposable soft contact lenses in both eyes.

Subjects must be screened according to the full list of inclusion/exclusion criteria in Section 1 of this protocol. Rescreening of subjects is not allowed in this study.

3.5 Outline of Study

This will be a prospective, randomized, crossover, double-masked study comparing 2 contact lenses. The expected duration of subject participation in the study is approximately 20 days, with 3 scheduled visits. The study is expected to be completed in approximately 5 weeks.

4 TREATMENTS ADMINISTERED

This is a crossover study design. Subjects will be randomized to 1 of the 2 lens sequences, as described below:

Sequence 1: DD T2 → Clariti 1 Day

Sequence 2: Clariti 1 Day → DD T2

4.1 Identity of Study Treatments

Table 4-1 Description of Test and Control Products

	Test Lens	Control Lens
LID Number	LID006841	LID014044
Lens	DD T2	Clariti 1 Day
Material	██████	somofilcon A
Water Content	██████	56%
Base Curve (mm)	8.3	8.6
Diameter (mm)	14.2	14.1
Rx powers to be available in this study	-1.75 to -4.50 D (0.25 D steps)	-1.75 to -4.50 D (0.25 D steps)
Packaging, Labeling, and Supply	
 • Blister foil pack • Foil label includes at a minimum: 
 - material name and/or identifier - base curve - diameter - manufacturing protocol number - packing solution - power - lot number - expiration date - content statement - investigational device statement - Sponsor information - country of origin • Provided in boxes of 12 lenses per power per box, identified with the following at a minimum: 
 - a color coded label stating the protocol number - identifier - power - an investigational use only statement - tracking number • Lenses should be stored at room temperature. 	
 • Blister foil pack • Foil label includes at a minimum: 
 - material name and/or identifier - base curve - diameter - packing solution - power - lot number - expiration date - content statement - investigational device statement - Sponsor information - country of origin • Provided in boxes of 12 lenses per power per box, identified with the following at a minimum: 
 - a color coded label stating the protocol number - identifier - power - an investigational use only statement - tracking number • Lenses should be stored at room temperature.
Usage	
 • Wear: 
 ○ Daily wear ○ Bilateral, crossover group • Replacement period: Daily Disposable • Exposure: At least 8 hours per day, at least 5 days per week over the study treatment duration. • Lens Care: N/A 	

4.2 Accountability Procedures

Upon receipt of the study lenses, the Investigator or delegate will conduct an inventory. Designated study staff will provide the study lenses to the subjects in accordance with their randomization schedule. Throughout the study, the Investigator or delegate must maintain records of study treatment dispensation and collection for each subject. This record must be made available to the study monitor for the purposes of verifying the accounting of clinical supplies. Any discrepancies and/or deficiencies between the observed disposition and the written account must be recorded along with an explanation.

It is the Investigator's responsibility to ensure that:

[figure not shown]

- All study products are accounted for and not used in any unauthorized manner
- All used foils and unused supplies are returned by each subject
- All unused products are available for return to the Study Sponsor, as directed
- Any study lenses associated with a device deficiency or with any product-related adverse event [ie, ADE or SADE] are returned to the Study Sponsor for investigation. Refer to Section 7.3 of this protocol for additional information on the reporting of device deficiencies and AEs and the return of study products associated with these events.

